6.0 Enrollment/Randomization

6.1. Screening and Obtaining Informed Consent. Patients will be identified at their clinic visits to a surgeon to schedule a resection of an eligible malignancy. Study staff will determine eligibility. When an eligible patient is identified (i.e., inclusion criteria are met and no exclusion criteria are present), informed consent will be pursued. Additionally, the patient will identify a caregiver who will be the subject for caregiver evaluation and will be the contact person in later phases of the study if the patient is unable to respond for him or herself. In some cases, the main caregiver may change due to various circumstances and a new caregiver will be contacted. Patient will be randomized and assigned via randomization to the Intervention Group or the Control Group.

To maintain group balance among types of malignancy, a critical determinant of outcome, the treatment group allocation will be specified by stratified randomization. We will randomize patients meeting all eligibility requirements in a 1:1 ratio to early PCC or standard of care using a computer-generated randomization scheme using a permuted block design, stratified by type of cancer. The randomization scheme will be created by the trial's primary biostatistician and be directly uploaded into REDCap's randomization module. In rare cases some patients may be enrolled into trial but not randomized for uncontrollable reasons such as a surgery date is talked about with patient with the expectation that surgery may not occur due to lack of response to a therapy. Some surgeons have tight windows of time scheduling the patient a few days after a scan which gives little room to meet with patient to consent and complete pre-surgery interventions. It will be rare (<10% of patients enrolled) that a patient is consented without randomization but the study team wants the option to connect with these patients when it is most convenient for them. The goal is to have 236 randomized patients with the expectation that more than 236 patients may be enrolled/consented to get to a total of 236 patients randomized.

6.2 Blinding. The post-op assessments of patients will be completed by a masked outcome assessor who is not aware of randomization assignments of patients. The assessors will be trained to avoid discussing assignment during their interactions with subjects.

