7.0 Study Procedures

7.1 Enrollment. After informed consent is obtained, on the day of enrollment baseline demographic, clinical, and psychometric data will be collected on all consented subjects if feasible. If baseline information is not obtained on consent day, it will be completed as soon as possible and always before scheduled operation date.

The following procedure will be conducted:

A **baseline function assessment** form will ascertain important information about the patient's baseline functional status, including history of depression and anxiety. Quality of life will be measured.

7.2 Intervention Trial. The Intervention Trial Phase will comprise of the Pre-operative Phase, In-Patient Phase, and the Long-Term Follow-up Treatment Phase. Patients in the control group will receive routine care for their malignancy and can receive palliative care consultation at the discretion of their providers. Patients assigned to the intervention group will be immediately scheduled for a preoperative outpatient palliative care consultation by a physician or

nurse practitioner on the Vanderbilt palliative care team. This encounter will focus on advance care planning, helping the patient articulate goals of care, and addressing any symptoms the patient is experiencing. If the patient is unable to come for the scheduled in-person consultation, a provider will contact them by phone to provide a phone consultation. Intervention patients will be compensated with a \$50 gift card or check for coming to the pre-operative in person palliative care visit. Patients in the intervention group will also receive an inpatient palliative care consultation at least twice weekly during post-op hospitalization focusing on pain and symptom management and addressing any psychosocial distress around the operation. While inpatients, the palliative care team will follow these patients at the discretion of the palliative care provider.

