*Abbreviations (alphabetical): **AD8**- Alzheimer Disease, **ASA**-American Society of Anesthesiologists, **DUREL**- Duke University Religion Index , **ER** – Emergency Room, **FACT-G**-Functional Assessment of Cancer Therapy - General, **TOI**-Trial Outcome Index, **FATE-S**-Family Assessment of Treatment at End of Life Short Form, **HCAHPS**-Hospital Consumer Assessment of Healthcare Providers and Systems , **LOS**-Length of Stay, **PROMIS**-Patient-Reported Outcomes Measurement Information System , **PS**-Performance Status , **PTSD**- Post Traumatic Stress Disorder, **Rx**- Prescription

7.2.2 Interventional Trial: Follow-up Phase. We will evaluate outcomes among survivors, approximately **90 days** after operation. The follow-up team will be blinded to patient assignment and will be instructed to avoid having patients reveal treatment group. Under the direction of the Vanderbilt Coordinating Center's lead neuropsychologist, trained study personnel will assess patients using the following validated telephone assessments:

- [1] Functional Assessment of Cancer Therapy-General (FACT-G) Trial Outcome Index (TOI) assessing functional status.
- [2] Karnofsky performance status assessing functional status.
- [3] FACT-G assessing Quality of Life
- [4] PROMIS Anxiety-6 assessment
- [5] PROMIS Depression-6 assessment
- [6] HCAHPS Question 21 assessment of satisfaction with hospital stay.
- [7] Days alive at home without an Emergency Room (ER) visit
- [8] Initiation of appropriate adjuvant therapy

At approximately 30, 60, and 90 days after the operation, study subjects will be contacted by the research personnel who will inquire about hospitalizations and ER visits and whether patients have initiated chemotherapy or radiotherapy since the operation; these data will be supplemented and corroborated by searches of the VUMC electronic medical record. Because adjuvant therapy is not the optimal therapeutic approach in all patients with these malignancies (some for instance, may require neo-adjuvant therapy that obviates adjuvant therapy), the medical records of all subjects will be examined by an oncologist to determine whether adjuvant therapy would be recommended based on any preoperative treatment and the results of the operation, assuming that the patient's functional status would allow it. The initiation of adjuvant therapy would then

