be an outcome for this subgroup of patients. There is also one small subgroup of patients that will have fatigue examined closer at baseline and 30 days after the operation.

At the 90 day assessment the assessors will administer the psychometric instruments listed above to access the 90 day outcomes. Patients who cannot be reached by phone will have hard copy assessments mailed to them and/or electronic versions sent by e-mail with links to the instruments in REDCap.

We will evaluate long-term outcomes among survivors, approximately **180 days** after operation.

- [1] PTSD Checklist-Civilian Version
- [2] FACT G TOI and Karnofsky Performance Status
- [3] Life Space Assessment Questionnaire
- [4] FACT-G
- [5] Trend in employment
- [6] Zarit Burden Interview
- [7] Trend in long-term care residence
- [8] Overall Survival
- [9] Trend in hospital admissions and in ER visits

At approximately 180 days after the operation, the outcomes assessor will again contact the subjects and will inquire about hospital admissions, ER visits, the patient's employment status (full-time, part-time, none) and whether the patient still lives at home or in a long-term care facility. At this time point, instruments to evaluate PTSD, post-traumatic growth, functional status, and quality of life will be administered. Additionally, the assessor will administer the Zarit Burden instrument to the caregiver. At approximately every 6-months thereafter patients and/or caregivers will be contacted, and functional status, life-space, quality of life, employment, long-term facility residence, hospital admissions, and ER visits along with caregiver burden will be assessed. Follow-up will continue for three years. Information about survival will be monitored by periodic surveillance of the medical record for indication of patient deaths as well as by newspaper searches of obituaries. If a scheduled 6-month contact occurs for a patient of whose death the study personnel were unaware, information about date of death will be obtained from the patient's caregiver.

When it is determined that a subject has died, the study personnel will contact the subject's designated caregiver to determine the end of life care utilization: whether and when the patient enrolled in hospice, when the patient's last dose of chemotherapy occurred, hospital admissions

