14.0 Content Analysis of Psychosocial Stressors

14.1 Description: To better understand the psychosocial stressors patients experience pre-operatively, the investigators will perform a content analysis of notes on the first 50 patients enrolled in the intervention arm with a preoperative palliative care consultation. The investigators will extract the text of the palliative care consultation notes relating to psychosocial distress along with basic demographic information on these patients, including, age, sex, race, ethnicity, and surgery type to create a deidentified Microsoft Excel document with these elements. Two investigators will read the extracts on this document and jointly develop a code book of themes for analysis. The two investigators will then independently code the deidentified note texts and then assess intercoder reliability. If intercoder concordance is less than 80%, they will discuss and recode until 80% concordance is reached. Once this concordance rate is reached, the investigators will perform a qualitative content analysis of the coded text to explore common themes.

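### No masking or record restriction is stated for the oncologist who defines the subgroup for the exploratory adjuvant-therapy endpoint

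*Combined protocol and SAP*

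**What the plan says.** Section 7.2.2 recognises that adjuvant therapy is not suitable for every patient. It therefore provides that "the medical records of all subjects will be examined by an oncologist to determine whether adjuvant therapy would be recommended". The basis of that judgement is given: "based on any preoperative treatment and the results of the operation, assuming that the patient's functional status would allow it". Starting adjuvant therapy would then "be an outcome for this subgroup of patients".

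Two passages deal with masking. Section 6.2 states: "The post-op assessments of patients will be completed by a masked outcome assessor". Section 7.2.2 blinds the follow-up team, which carries out the telephone assessments. Neither passage names the oncologist.

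On what the record contains, section 7.2.2 says of patients' reports of hospital use, chemotherapy and radiotherapy that "these data will be supplemented and corroborated by searches of the VUMC electronic medical record". Section 7.2 adds: "Patients in the intervention group will also receive an inpatient palliative care consultation at least twice weekly during post-op hospitalization". It also provides for a preoperative consultation and three outpatient contacts in the first 90 days. Section 14 (content analysis) shows that written notes of the preoperative consultation exist: "The investigators will extract the text of the palliative care consultation notes relating to psychosocial distress".

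The Aim 1 text calls the adjuvant endpoint exploratory. Section 4.2.3 lists it as time from surgery to adjuvant therapy and does not mention the subgroup. Section 10.1 says that the study is not powered for secondary or exploratory outcomes.

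**The concern.** One reader's judgement settles who is counted for this endpoint. It uses the results of the operation, so it necessarily comes after randomisation. If that reader can see the arm, or whether the patient went on to adjuvant therapy, membership of the subgroup may depend on either, and the comparison within it loses the protection of randomisation.

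There is a plausible route by which this could differ between arms. The intervention includes goals-of-care discussions, so one arm is likely to have more written material on patients' preferences. A patient who did not start therapy, and whose notes record a considered refusal, might more readily be judged not to have had an indication. Removing such patients from one arm raises its apparent initiation rate with no true effect. Other errors, or the same error in the control arm, would move the comparison the other way.

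What is at stake is how one exploratory comparison between the arms can be interpreted.

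**Working it through.** **1. Who is masked.**

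| Role | Section | Masking stated? |
|---|---|---|
| Outcome assessor for postoperative assessments | 6.2 | Yes |
| Follow-up team (telephone assessments) | 7.2.2 | Yes |
| Oncologist judging whether adjuvant therapy would be recommended | 7.2.2 | Not stated |

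Nor does the text limit which parts of the record the oncologist reads, set a cut-off date, or say that the judgement comes before adjuvant treatment is known.

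**2. Can the record show the arm?** Very probably. Intervention patients have repeated scheduled contacts with palliative care providers at the same institution, and consultation notes exist (sections 7.2 and 14). Section 12.2 reports, from the institution's electronic record, that fewer than 10% of comparable patients receive palliative care consultation at any point. Such a note is therefore a strong, though imperfect, marker of arm.

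**3. Can the record show the outcome?** Possibly. The same record system is used to corroborate whether chemotherapy or radiotherapy began. Treatment given elsewhere may be missing from it.

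**4. Is there a figure to reproduce?** Not for this endpoint: the documents give neither the share of patients with an indication nor an initiation rate. The only sample-size calculation (section 10.1) is for the primary endpoint. It reproduces, at 98 per group for a difference of 7.28 and a standard deviation of 18.1, and this point does not bear on it.

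**5. Hypothetical size.** From the documents: 118 patients per arm. Assumed, and not in the documents:
- share with a true indication, e = 40% to 80%, giving N = 118 × e = 47 to 94 per arm;
- true initiation rate, p = 50% to 70%, the same in both arms;
- share of non-starters wrongly excluded in one arm only, m = 5%, 10% or 20%.

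The apparent rate in the affected arm is p′ = p / [p + (1 − p)(1 − m)]. It does not depend on e.

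| p | m = 5% | m = 10% | m = 20% |
|---|---|---|---|
| 50% | 51.3% (+1.3) | 52.6% (+2.6) | 55.6% (+5.6) |
| 60% | 61.2% (+1.2) | 62.5% (+2.5) | 65.2% (+5.2) |
| 70% | 71.1% (+1.1) | 72.2% (+2.2) | 74.5% (+4.5) |

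For example, with p = 60% and m = 20%: 0.6 / (0.6 + 0.4 × 0.8) = 0.6 / 0.92 = 65.2%.

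**6. Effect on a nominal 5% two-sided test of two proportions.** Let n′ = N[p + (1 − p)(1 − m)], SE = √[p(1 − p)/N + p′(1 − p′)/n′] and z = (p′ − p)/SE. The rejection rate is 1 − Φ(1.96 − z) + Φ(−1.96 − z).

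With e = 60%, p = 60% and m = 20%: N = 70.8, n′ = 65.1, SE = 0.083, z = 0.052/0.083 = 0.63, and the rejection rate is 9.6%. Over the whole grid it is 5.1% to 5.4% for m = 5%, 5.6% to 6.5% for m = 10%, and 7.7% to 11.6% for m = 20%.

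**7. Limits of the illustration.** With equal true rates, the same m in both arms cancels. Applying m to the control arm instead reverses the sign. The calculation uses a simple proportion, whereas section 4.2.3 lists a time to event and section 10.1 plans Kaplan-Meier, log-rank and Cox methods for such outcomes. It shows the mechanism, not the size of bias in the listed analysis.

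**The case against.** The strongest reply is that the protocol already states what the judgement rests on: preoperative treatment and operative results, with functional status set aside. The question is whether therapy would be recommended, not whether the patient wanted it. For a recorded refusal to count as no indication, the oncologist would have to depart from that rule, and nothing in the documents suggests this would happen. This stands as a real partial safeguard. But it governs the reasoning, not what the reader sees, and no written decision rules by tumour type accompany it although the eligible operations are varied.

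Second, the blinding provisions extend beyond section 6.2. Section 7.2.2 blinds the follow-up team and lists adjuvant therapy among that team's items, and section 7.6 charges the coordinating centre with maintaining blinding. That is correct, but neither provision names the oncologist or describes the record review as masked.

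Third, the endpoint is exploratory and unpowered, and any shift is small beside its sampling error. With about 71 per arm and a 60% rate, the standard error of the difference is √(2 × 0.24/71) = 0.082, or about 8 points, giving a 95% half-width of about 16 points. This stands, and it limits the importance of the point.

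A reader might infer more: that the oncologist reads the whole record and knows the outcome, and that the result is therefore biased in favour of palliative care. The documents do not support that. They refer to medical records without saying how much is read or when. Outcome data come first from patients by telephone, and treatment elsewhere may not appear in the institution's record. Control patients may also decline therapy and have this noted, so the direction is not determined.

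**Conclusion.** The point holds as an unguarded risk, not as a demonstrated bias. A post-randomisation judgement defines the analysis subgroup, and no masking, record restriction or order of review is stated for the person who makes it. That the record reveals the arm is a strong inference; that it reveals the outcome is a weaker one. The stated criteria lessen the risk without removing it.

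The size and direction cannot be calculated from the documents. The shift of about 1 to 6 points rests wholly on assumed rates and on errors confined to one arm. Only the exploratory adjuvant-therapy endpoint is concerned. The primary endpoint and the secondary endpoints in section 4.2.2 do not use this subgroup. The point is still worth acting on, because the remedy merely enforces the protocol's own criteria with the same reader.

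**What to change.** In section 7.2.2, state that the same oncologist judges indication from an extract limited to cancer type, preoperative treatment, operative note and final pathology, masked to arm and to postoperative treatment. Staff preparing the extract should remove any mention of palliative care. Record the judgement in REDCap before data on the start of adjuvant therapy are linked. Extend section 6.2 to cover this step, and name the subgroup beside the endpoint in section 4.2.3 so that the analysis population is clear.

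The cost is modest staff time to prepare extracts for up to 236 patients, including obtaining records of preoperative treatment given elsewhere, and one added step in the database. No extra reader, patient contact or change in sample size is needed.

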4.2.3 Exploratory Endpoints

- [1] FACT-G TOI score [180 days, trend over study period]
- [2] FACT-G score [180 days, trend over study period]
- [3] PROMIS Anxiety-6 score [90 days, 180 days]
- [4] PROMIS Depression-6 score [90 days, 180 days]
- [5] Satisfaction with hospital stay [30 days]
- [6] Time from surgery to adjuvant therapy
- [7] Overall Survival [3 years]
- [8] Post-traumatic Growth Inventory score [180 days]
- [9] Karnofsky Performance Status [90 days, 180 days, trend over study period]
- [10] Employment [trend over study period]
- [11] Number of hospital admissions over study period
- [12] Number of ER visits over study period
- [13] Long-term care residence [trend over study period]
- [14] Life Space Assessment Questionnaire score [trend over study period]
- [15] Zarit Burden Interview [90 days, 180 days, trend over study period]

4.2.4 Planned Subgroup Analysis: Patients who die during the course of the study will be included in a subgroup analysis with the following outcomes.

- [1] Receipt of chemotherapy within 14 days of death
- [2] Hospice enrollment of less than 7 days before death
- [3] Days at home without ER visit or hospital stay in last 30 days of life
- [4] Location of death (home vs. facility)
- [5] Quality of end-of-life care (FATE-S score)

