and ER visits in the last month of life, and where the patient died. Additionally, a quality of death and dying survey will be administered to the caregiver

7.3.1 Long-term Follow-Up Patient Retention Plan. In order to maximize full participation of the randomized patients, the Long-Term Follow-Up Committee will rely on strategies refined over the past 15 years to produce a Follow-Up assessment rate of >85%. Study personnel will be instructed to obtain as much contact information as possible at time of enrollment (e.g. multiple phone numbers, mailing addresses, discharge destination etc.). The Neuropsychology Coordinator will perform the following interventions to maintain >85% Follow-Up assessment rates:

- [1] A periodic phone call or letter will serve as an additional reminder of study participation.
- [2] Weekly meetings will be conducted with study staff to evaluate the status of follow-up evaluations, with a particular focus on devising and implementing effective strategies to reach patients who may be difficult to contact. In rare situations, home visits may be conducted to help complete assessments.
- [3] Participants will be compensated a \$50 gift card or check after they complete the 90 day phone assessment.
- [4] Participants may be contacted by SMS text messaging to arrange times to perform assessments or to remind participants to complete electronic versions of assessments. When contacting participants by text, study staff will identify themselves in a message with no PHI and then ask participants to confirm their identity before communicating any potentially identifiable information.

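### For patients who die between late follow-up contacts, the described caregiver call covers admissions and ER visits only in the last month, so study-period counts may miss up to about five months of use

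*Combined protocol and SAP*

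**What the plan says.** Section 4.2.3 defines two exploratory endpoints as whole-study counts: "Number of hospital admissions over study period" ([11]) and "Number of ER visits over study period" ([12]).

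Section 7.2.2 describes how the events are collected:

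- **Early contacts.** The text reads "At approximately 30, 60, and 90 days after the operation, study subjects will be contacted by the research personnel who will inquire about hospitalizations and"; the sentence then goes on to name emergency visits. For this block the plan adds that "these data will be supplemented and corroborated by searches of the VUMC electronic medical record".
- **Day 180.** "At approximately 180 days after the operation, the outcomes assessor will again contact the subjects and will inquire about hospital admissions, ER visits".
- **Later.** "At approximately every 6-months thereafter patients and/or caregivers will be contacted", with admissions and ER visits among the items assessed, until three years.
- **After a death.** The designated caregiver is contacted about end-of-life care. The questions cover hospice, last chemotherapy, hospital admissions "and ER visits in the last month of life, and where the patient died".

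If a scheduled six-month contact reveals a death that staff did not know of, 7.2.2 names only the date of death as the information to obtain at that step. In long-term follow-up the stated purpose of watching the medical record is to detect deaths.

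Section 4.2.4 contains the outcome that the one-month look-back fits: "Days at home without ER visit or hospital stay in last 30 days of life".

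**The concern.** The one-month look-back suits the end-of-life outcome in 4.2.4 but not a count over the whole study period. After day 180 the contacts are about six months apart. A patient interviewed at month 12 who dies at month 17.5 has the last month covered by the caregiver call, while no described question covers months 12 to 16.5.

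Events that nobody asks about can only lower a count, and the unasked months fall in the run-up to death, when hospital use may well be high. If the form stores no reported events as zero, the multiple imputation planned in Section 10.2 would not be triggered. Dividing the count by time alive would not repair the loss either, because the denominator would include months for which no events were sought.

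**Working it through.** The plan gives no figure for this gap, so there is none to reproduce. The check is interval arithmetic on the contact schedule.

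**Inputs from 7.2.2.** Contacts at about days 30, 60, 90 and 180, then about every six months (taken as 182.5 days) to three years. Look-back after death: one month, taken as 30 days.

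**Assumptions.** Contacts are completed on schedule, and death falls uniformly within an interval.

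**Formulas.** For an interval of L days with L of at least 30:

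- maximum unasked time = L − 30
- share of deaths with any unasked time = (L − 30)/L
- mean unasked time over all deaths in the interval = (L − 30)²/(2L)
- mean time since last contact = L/2

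**Results.**

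| Death falls in | L (days) | Maximum | Share with a gap | Mean gap | Mean gap ÷ (L/2) |
|---|---|---|---|---|---|
| Days 0–30, 30–60, 60–90 | 30 | 0 | 0% | 0 | 0% |
| Days 90–180 | 90 | 60 | 60/90 = 67% | 60²/180 = 20.0 | 20/45 = 44% |
| Each later six-month interval | 182.5 | 152.5 | 152.5/182.5 = 84% | 152.5²/365 = 63.7 | 63.7/91.25 = 70% |

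In months, with a six-month interval and a one-month look-back, the mean is 5²/(2 × 6) = 25/12 = 2.08 and the maximum is 5.

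The first gap appears for deaths after about day 120: the day-90 contact plus the 30-day look-back.

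**Effect on the counts.** The documents give neither an event rate before death nor the share of events that the VUMC record would show. Assume 0.1 to 0.4 events per month and 0 to 80% found in the record. Missed events per patient dying after day 180 = rate × (63.7/30.4 = 2.10 months) × (1 − capture):

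- lowest: 0.1 × 2.10 × 0.2 = 0.04
- middle: 0.2 × 2.10 × 0.5 = 0.21
- highest: 0.4 × 2.10 × 1 = 0.84

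At the maximum gap (152.5/30.4 = 5.02 months) the range is 0.1 × 5.02 × 0.2 = 0.10 to 0.4 × 5.02 × 1 = 2.0. No trial total is given, because the documents state no expected number or timing of deaths.

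**The case against.** **Other sources may fill part of the gap.** Section 11 says in general that most data come from medical records or direct assessments, so VUMC events may be found anyway. The six-monthly contact may go to a caregiver, and the text does not say that the usual utilisation questions are dropped when that contact uncovers a death. This stands in part. The loss is possible rather than certain, and it is likelier for care outside VUMC. But the plan commits to a utilisation search only for the first 90 days, and at a contact that reveals a death it names only the date.

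**The data timeline might settle it.** The Section 7.2 table has a post-mortem column and rows for ER visits and unplanned admissions, but the shading of those rows is not readable in the text available here. It could show that the items are collected after death. It would not change the stated one-month look-back.

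**Imputation and person-time could handle it.** Section 10.2 names death as a cause of missing data, and person-time can be restricted to observed windows. Both work only if the unasked window is recorded as missing.

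**The endpoints are minor.** This stands. Two of 15 exploratory endpoints are touched, and Section 10.1 says that the study is not powered for them.

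A reader might also infer two stronger claims:

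- *Nursing-facility or inpatient-hospice days would count as days at home in the last 30 days.* The documents do not support this. The 4.2.4 outcome already requires being at home, and the data timeline lists hospital or facility length of stay and hospice length of stay.
- *The loss is unequal between arms because Section 7.2 plans a palliative care visit at each later Vanderbilt admission in the intervention arm.* No mechanism is shown. If the record is not searched, such a visit does not reach the blinded assessor's count. If it is searched, Vanderbilt admissions appear in both arms.

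**Conclusion.** The point holds in limited form, as a minor one. As 7.2.2 is written, use between the last completed contact and the final month of life is not asked about for deaths after about day 120 that fall more than a month after a contact. In the six-month intervals after day 180 this is 84% of deaths, and the mean gap over all deaths there is about 70% of the time since the last contact. A missed contact before death would lengthen the gap.

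Counts for endpoints [11] and [12] in these patients may be too low. The size in events rests entirely on the assumed rates and record capture, and its lower end is negligible. It would be wrong to conclude that counts are too low in all patients who die: deaths up to about day 120, and later deaths within a month of a completed contact, have no gap on schedule.

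The primary endpoint and the secondary endpoints, including days alive at home in the first 90 days, are not affected. The one-month look-back is adequate for admissions and ER visits in the last-30-days outcome.

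**What to change.** In 7.2.2:

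1. Have the post-mortem caregiver call ask for dated hospital admissions and ER visits since the last completed study contact, flagging those in the last 30 days of life. This serves both the study-period counts and the end-of-life outcome.
2. State that the VUMC record search for admissions and ER visits runs to death or end of follow-up, in the same way in both arms.
3. Where the earlier window cannot be recovered, record it as missing rather than as zero events, and limit person-time to the observed windows.

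The cost is a wording change to an existing call, one REDCap form and a longer record search. The call becomes slightly longer, and the caregiver must recall up to about six months, the same span as at the biannual contacts.
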